# 6.3 INELIGIBLE AND NON-RECRUITED PARTICIPANTS

Details will be maintained as above for ineligible participants including reason for ineligibility, and these patients will be treated as per local guidelines.

For participants who consent to participation but who are not randomised, reason for this will be recorded in the screening log e.g. Participant withdrew consent or delivered prior to administration of first dose of intervention. This is a feasibility study and the barriers to recruitment and participation are collected in order to assess the impact of a potentially larger trial.

# 6.4 CONSENTING PARTICIPANT

Women who appear eligible for the study after the screening assessment will be provided with further information about the study in the form of a copy of the written information sheet in English and Chichewa. All written information will be read to the woman in full by either the investigator or delegate who may be a Community educator/nurse. An independent witness will be requested for women with low literacy skills. Women will then be given a suitable period of time (usually a minimum of 24 hours) to consider if they would like to participate in the study and to talk to their husbands and other family members if they wish. Interested women will usually be asked to attend the clinic the following week. However, many women travel long distances to attend antenatal care and if she prefers, the woman may waive the time to consider the study, and consent at the first study visit. This will be recorded on the eCRF.

Women who are willing to participate will be asked to provide written informed consent prior to undertaking any study procedures. Women with low literacy skills may need to sign the consent form using a thumb print (preferred). In this scenario an independent witness will be sought to countersign the consent form to confirm that the woman appears to have given consent and that she appears to understand the nature of the study and what she is being asked to do. Women who undergo the informed consent process and provide a written consent will then undergo screening for eligibility determination.

# 7. RANDOMISATION

#### 7.1 Randomisation Procedures

Participants will be randomised to treatment (active or placebo) in a 1:1 ratio. Recruiting centre will be the only stratification variable, using simple randomisation under a randomly permuted block design. Randomisation codes will be provided by ECTU to ISG and packs dispensed in a sequential fashion. Details of the study pack number allocated will be recorded in the participant's medication record as well as in the drug accountability logs.

# 7.2 EMERGENCY UNBLINDING PROCEDURES

In a clinical emergency, where continued treatment with metformin is considered potentially harmful by the woman's attending clinician, participating women should be treated as if they were taking the active treatment (metformin) and should stop the study treatment. It is anticipated that breaking of the study blind should be performed only where knowledge of the treatment is absolutely necessary for further management of the participant. It is not anticipated that the development of gestational diabetes will be an indication for unblinding as the study treatment must stop, as described in paragraph 5.9.

The on-site pharmacy will hold the unblinding information. Thus unblinding (emergency or otherwise) can be carried out locally by a pharmacist, if requested by a senior clinician (normally a consultant). This unblinding process will be available during normal working hours. A 24/7 telephone unblinding will also be available. In the case of any unblinding, the name of the clinician requesting the unblinding and the reason for it will be sent to the sponsor's representative via e-mail, who will inform the CI. In case of a SUSAR, the sponsor will contact ECTU for the unblinding code for that participant.

The reasons for unblinding will be documented and added to the eCRF. Unless there is a clinical requirement, the blind will not be broken to any member of the trial team until after data entry is complete and the database locked. Details of the unblinding will be kept in pharmacy.

# 7.3 WITHDRAWAL OF STUDY PARTICIPANTS

Participants are free to withdraw from the study at any point if they wish. Additionally, a participant can be withdrawn by the Investigator.

If withdrawal occurs, the primary reason for withdrawal will be documented in the participant's medical records and eCRF, if possible. The participant will have the option of withdrawal from:

- (i) Taking the study medication, with continued study procedures and collection of clinical and safety data.
- (ii) All aspects of the trial. In this scenario, study teams can continue to use data collected up to that point

If a participant wishes to withdraw from the trial (or if the investigator advises withdrawal). The trial team will be informed and withdrawal will be recorded in the medical notes and eCRF, along with the aspects from which they wish to withdraw.

### 7.4 CESSATION OF STUDY MEDICATION

Medication (but not study participation) will be stopped in any of the following circumstances:

- Fetal demise in utero
- Diagnosis of diabetes (gestational or otherwise)
- If the participant develops severe pre-eclampsia or HELLP syndrome
- Delivery of the baby (end of pregnancy)
- If the clinical team judge that immediate delivery is advised in the next 48 hours, for example in the case of development of severe sepsis or evidence of fetal compromise.

Metformin should be stopped temporarily if any of the following occur:

- Elective surgery (metformin should be stopped 48 hours prior)
- Severe diarrhoea or vomiting or fever
- Reduced fluid intake
- Non steroidal anti-inflammatory drug therapy for more than two days

Metformin can be restarted once the event/ episode above has ceased:

Participants who stop treatment following administration of the first dose of intervention or any doses thereafter will not be replaced by additional recruited participants. Where possible, data will continue to be collected from all participants after initial enrolment to allow intention to treat analysis.

#### 8. STUDY DRUG

Active drug: Metformin (Glucophage) 500mg slow release film-coated tablet up to 2000 mg per day

**Placebo:** Placebo tablets will be identical to the active tablets except for the active ingredient.

Both placebo and active drugs will be supplied by Merck KGaA.

#### 8.1 INVESTIGATIONAL MEDICINAL PRODUCT AND PLACEBO

#### 8.1.1 Study Drug Manufacturer

Active and placebo drug: Merck Santé

[name],

[name],

France

# 8.1.2 Marketing Authorisation Holder

Active drug: Glucophage XR 500 mg: A39/21.2/0027 Placebo: Not Applicable

# 8.1.3 Labelling and Packaging

Both the active and placebo treatments will be labelled and packaged in high density polyethylene (HDPE) bottles by Investigational Supplies Group (ISG), [name] in accordance with the Pharmacy, Medicines and Poisons Board (PMPB). Drugs will be supplied in bottles each containing Glucophage 500 mg slow release tablets or placebo sufficient bottles for one month supply will normally be dispensed to a participant at any one time.

# 8.1.4 Storage

This IMP requires storage store at or below 30 °C.

# 8.1.5 Regulatory Release to Site

This will be performed by the QP from ISG. A working practice document will be generated to clarify how the drug will be distributed.

# 8.1.6 Destruction of Trial Drug

Destruction of trial drug will be conducted in Malawi in accordance with the local PMPB procedures.

# 8.1.7 Summary of Product Characteristics (SPC) or Investigators Brochure

A Summary of Product Characteristics (SPC) is available in a separate SPC booklet.

Licensed indications are for the treatment of type 2 diabetes mellitus in adults (including pregnant women for pre-existing diabetes and Gestational diabetes) particularly in overweight patients, when dietary management and exercise alone does not result in adequate glycaemic control. Metformin will not be used within its licensed indications for this study. In the UK, Glucophage® SR is also licensed for a reduction in the risk or delay of the onset of type 2 diabetes mellitus in adult, overweight patients with impaired Glucose Tolerance and /or Impaired Fasting Glucose, and/or increased HbA1C (glycated haemoglobin).

Contraindications are noted in the exclusion criteria for this study.

# 8.1.8 Information on the label.

Medication labels will be (English and Chichewa) and comply with the legal requirements of Pharmacy Medicines and Poisons Board (PMPB) and ICH GCP. They will include storage conditions for the drug, but no information about the participant. Pictures will also be included in the labels to show participants how many tablets to take and when to take them i.e. sunrise and sunset etc.

# 8.2 DRUG DISPENSING

Drug stocks will be held by the local pharmacy departments and transported to the clinical areas or given directly to the participant after randomisation, as appropriate. Following randomisation, the next sequential pack as allocated will be detailed in the

accountability log and removed from the supply shelf. All treatments will be dispensed by authorised staff and prescribed a physician. Following dispensing, the first dose will be administered to the participant in a timely fashion, ideally on the same day or within 48 hours. There will be space in the participants' daily diary to record the dose administration.

# 8.3 DOSING REGIME

Women will be prescribed metformin tablets in an incremental dose starting at 500mg (1 tablet per day) increasing over four weeks up to 2000mg (4 tablets per day).

First dose will be administered following consent (first visit between 12 and 28 weeks gestation). Women will be asked to start (week 1) with 500mg metformin (1 tablet, once daily) taken with food in the evening, increasing in week 2 to total daily dose of 1000mg per day (2 tablet, one in the morning and one in the evening daily). In week 3: there will be a further increment to a total daily dose of 1500mg per day (3 tablets, one in the morning and two in the evening daily). In week 4 there will be a final increment to a total daily dose of 2000mg (4 tablets, two in the morning and two in the evening daily). Thereafter treatment is planned to continue at 2000 mg (4 tablets) until women have delivered their baby or met one of the criteria described paragraph 5.9.

Week	Morning Tablets (500mg each)	Evening Tablets (500mg each)
Week 1	0	1
Week 2	1	1
Week 3	1	2
Week 4	2	2
Week 5	2	2

If side effects (largely anticipated to be gastro-intestinal) are experienced, the woman or the woman's physician can adjust the dose to the previous week's dose or to 500mg metformin (whichever is the greater) and wait for a week before increasing the dosage again. They may also recommend to minimize adverse effects that the women take the treatment in the evening as the maximum recommended dose is 2000mg daily, taken as one dose in the evening.

# 8.4 DOSE CHANGES

The local investigator may alter the above treatment regimen at his/her discretion. Women may also be advised to take the medication as a single dose in the evening, if they prefer, provided the maximum daily dose does not exceed 2000mg. Changes to treatment dose will be recorded on the eCRF as soon as practicable. Where AE are considered by the participant or the local investigator to be excessive, the investigator (or participant) can adjust the IMP dose accordingly.

# 8.5 PARTICIPANT COMPLIANCE

Participants will be asked to keep a daily diary to record drug intake and to bring all medication including empty packaging to each study visit, so that the health care staff can record how much study drug has been taken.

Unused medication will be requested to be returned to the trial centre and individual tablets will be counted by pharmacy staff to ascertain the number taken.

# 8.6 PRECAUTIONS

**Overdose:** Hypoglycaemia has not been seen with metformin hydrochloride doses of up to 85g, although lactic acidosis has occurred in such circumstances. High overdose PAPAGENO: Protocol Version 1.0 07/03/2019

of metformin hydrochloride or concomitant risks may, very rarely, lead to lactic acidosis. Lactic acidosis is a very rare complication of metformin, occurring in less than 4 per 100,000 patients. Lactic acidosis is a medical emergency and must be treated in hospital. The most effective method to remove lactate and metformin hydrochloride is haemodialysis.

**Dehydration**: In case of dehydration (severe diarrhoea or vomiting, fever or reduced fluid intake), metformin should be temporarily halted and contact with a health care professional is recommended. Treatment may re-commence on advice of the local Principal investigator

### 8.7 Non-Investigational Medicinal Products

There are no NIMPs used in this CTIMP

#### 8.8 PERMITTED MEDICATIONS

All medications other than those detailed in the current SPC and 6.7.3 (prohibited medications) are permitted.

Medications that participants have been prescribed pre-pregnancy and which have been continued during the pregnancy as per the supervising physician responsible for participant care may be taken during the trial.

Women currently prescribed treatments for HIV will be permitted to join the study provided they have been taking HIV medication for greater than 6 months. Metformin is not currently known to interact with protease inhibitors or non-nucleoside reverse transcriptase inhibitors (NNRTIs). However, lactic acidosis a side-effect of some nucleoside reverse transcriptase inhibitors (NRTIs). Patients taking these drugs with metformin may be at an increased risk of lactic acidosis (HIV In site 2018 and HIV and Aids information 2018).

Lactic acidosis is a rare event estimated to be 3.3 to 4.3 per 100,000 patient years in patients treated with metformin (Lalau, JD. Drug-Safety 2010). However, in the event any woman experiences a major reduction in urinary output (e.g. output is less than 200ml per day) they should be advised **to stop the study treatments** immediately and seek Medical advice.

# 8.9 PROHIBITED MEDICATIONS

Should any of the below prohibited medications be inadvertently co-administered with the IMP, the participant should contact their obstetric team and attend for assessment as required.

- Alcohol and alcohol containing medicinal products since there is increased risk of lactic acidosis in acute alcohol intoxication, particularly in case of fasting, malnutrition, or hepatic insufficiency. Pregnant women should avoid alcohol in any case, so this is not likely to be a significant issue in practice.
- **Iodinated contrast agents** should also be avoided since intravascular administration of iodinated contrast agents may lead to renal failure, resulting in metformin hydrochloride accumulation and an increased risk of lactic acidosis. Thus any woman in the study who needs such an agent will be advised to discontinue metformin hydrochloride must be discontinued prior to, or at the time of the test and not restart metformin until 48 hours afterwards, and only after renal function has been re-evaluated and found to be normal.
- **Glucocorticoids** (systemic and local routes), beta-2-agonists, and diuretics may attenuate metformin's potential hypoglycaemic effect and ACE inhibitors may amplify it. Use of these agents is not prohibited but they should be used with care in women participating in this study and after discussion with the local principal investigator.

### 9. STUDY ASSESSMENTS

#### 9.1 SAFETY ASSESSMENTS

Safety will be assessed at each routine clinic visit and documented in the medical notes and eCRF. Serious Adverse Events (SAE) will be reported as described in section 12. However, the most common adverse reactions known to be caused by metformin are: nausea, vomiting, diarrhoea, abdominal pain and loss of appetite: most resolve spontaneously. We will record on the eCRF and reported as AE's any of these symptoms that have been experienced during the seven day period, preceding the study visit. Interim un-blinded outcome data will be made available to the Data Safety and Monitoring Committee (DSMC).

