# MONTHLY STUDY VISITS (+/- 7 days)

Approximately 1 month (plus or minus seven days) after the commencement of study treatment (and every 4 weeks thereafter until delivery) a study visit will be conducted. During the visit the study team will collect information on any side effects, adverse events and pregnancy complications.

Adverse events (AE) will be recorded in the eCRF, and serious adverse events (SAEs) will be recorded on the SAE form as per section 10. Patients will also be asked to return their empty medication packages and unused medication to each visit. They will be asked if they are complying with their study medication and the diary reviewed, if available.

A further drug supply (sufficient for up to 5 weeks of treatment) will be prescribed and dispensed at each study visit, as required.

The number of monthly antenatal study visits completed for each woman will depend on the gestation at which the woman was recruited i.e. if consented and randomised at 12 weeks we would anticipate 8 antenatal visits (consent at 12 weeks plus a monthly visit at each gestational time point: 16/20/24/28/32/36 and 40 weeks maximum) to be conducted and recorded.

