#### **10.2 DATA COLLECTION**

Data will be collected by the trial team from the participant verbally and confirmed where possible in the medical records including demographics, details of current and previous pregnancies, contact details, information about blood test collections, labour and delivery outcomes, and neonatal / postnatal outcomes. Participants will be asked about their well-being at each post-randomisation visit to identify side effects and any adverse events for reporting. We will also review diaries for compliance, acceptability and side effects. Results of study blood tests for glucose tolerance testing locally will remain concealed from the participant and her clinician until the trial is completed.

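### The seven-day recall rule for common metformin symptoms leaves at least 75% of the dose escalation outside its window and conflicts with the unrestricted side-effect capture elsewhere in the protocol

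*Protocol*

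**What the plan says.** Section 9.1 names the common reactions to metformin: "nausea, vomiting, diarrhoea, abdominal pain and loss of appetite: most resolve spontaneously". It then directs that the eCRF record, and the team report as adverse events, "any of these symptoms that have been experienced during the seven day period, preceding the study visit".

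The visit and dosing schedules that this rule meets are:
- **First on-treatment visit** (section 9.2, monthly study visits): "Approximately 1 month (plus or minus seven days) after the commencement of study treatment", then every four weeks until delivery.
- **Dose** (section 8.3): one tablet a day in week 1, two in week 2, three in week 3. Then "In week 4 there will be a final increment to a total daily dose of 2000mg".

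Other sections collect the same kind of information without a seven-day limit:
- Section 9.2, monthly visits: "During the visit the study team will collect information on any side effects, adverse events and pregnancy complications".
- Section 10.2: "We will also review diaries for compliance, acceptability and side effects".
- Section 12: women may report symptoms to the investigator whenever they arise, and experience of the common reactions is gathered monthly.
- Section 12.2: open questioning about adverse events at each visit, recording the event where there is doubt.
- Section 8.4: dose changes go on the eCRF.

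The trial summary lists adverse events by group among the secondary endpoints. Section 11.2 plans descriptive summaries by arm and no formal comparison.

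**The concern.** Section 9.1 is the only rule written specifically for these five symptoms, so site staff could reasonably take it as the one that governs the eCRF side-effect questionnaire in the table of study visits. If they do, the look-back at the first visit misses most or all of the weeks in which the dose is being raised. Section 8.3 places its own provision for gastrointestinal side effects in that period. Because the protocol says that most of these symptoms settle by themselves, an episode in week 1 or 2 may well be over before the window opens.

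At stake is the descriptive incidence of common symptoms in each arm, and so part of the tolerability information that section 11.1 intends to carry into a large trial. This is a rule about what is collected, so no later analysis can recover symptoms that were never recorded. If some staff apply the seven-day limit and others apply the open enquiry, the counts mix two recall periods and are hard to interpret.

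**Working it through.** The protocol gives no figure of its own to reproduce. The check is a count of calendar days.

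**Inputs**
- Day 1 = first dose.
- Planned escalation = weeks 1 to 4 = days 1 to 28. The steps below the final dose are weeks 1 to 3 = days 1 to 21 (section 8.3).
- First visit on day v = 21, 28 or 35. One month is read as 28 days because later visits are four-weekly, and the tolerance is 7 days (section 9.2).
- Recall window = days v − 6 to v (section 9.1).

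**Coverage of the escalation by the section 9.1 window alone**

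| First visit | Window | Escalation days covered | Lower-dose days covered |
|---|---|---|---|
| Day 21 | 15–21 | 7/28 = 25% | 7/21 = 33% |
| Day 28 | 22–28 | 7/28 = 25% | 0/21 = 0% |
| Day 35 | 29–35 | 0/28 = 0% | 0/21 = 0% |

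The uncovered share of the escalation is 1 − 7/28 = 75% at best and 100% at worst. The earliest day that any permitted first visit can reach is day 15, so weeks 1 and 2 are never inside the window. The second visit does not help: even if it came only three weeks after a day-21 visit, on day 42, its window would open on day 36.

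**Coverage over the whole of treatment.** With visits every 28 days, 7/28 = 25%. With intervals of 21 or 35 days, 7/21 = 33% or 7/35 = 20%.

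**What this could mean for one episode.** The protocol gives no data on onset or duration, so this is an illustration only. Assume a single episode of D days whose onset is equally likely on each of days 1 to 28. It touches the window if onset s satisfies s ≤ v and s + D − 1 ≥ v − 6. The chance is the number of such s in 1 to 28, divided by 28.

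| Duration D | Visit day 21 | Visit day 28 | Visit day 35 |
|---|---|---|---|
| 3 days | 9/28 = 32% | 9/28 = 32% | 2/28 = 7% |
| 7 days | 13/28 = 46% | 13/28 = 46% | 6/28 = 21% |
| 14 days | 20/28 = 71% | 20/28 = 71% | 13/28 = 46% |

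The range of 7% to 71% shows how far the loss depends on facts that the protocol does not supply.

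**Effect of a recall period running from the previous visit, or from first dose.** A day-28 first visit would cover 28 of 28 escalation days instead of 7. A day-35 visit would cover 28 instead of 0. A day-21 visit would cover days 1 to 21, and the next visit would cover days 22 to 28.

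**The rules side by side.** Vomiting on day 5 that has stopped by day 7 is an adverse event under the definition in section 12.1 and is within the open enquiry of section 12.2. It lies outside the section 9.1 window at every permitted first visit. The protocol does not say which rule decides whether it is recorded.

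**The case against.** A reader might infer that these symptoms are recorded only in the seven-day window, that most of the escalation is never observed, and that tolerability is therefore overstated. The documents do not support that. Section 9.1 does not say that its window is the sole route. Sections 9.2, 10.2, 12 and 12.2 all allow earlier symptoms to be captured, and a step-down in dose during weeks 1 to 3 should appear on the eCRF under section 8.4. A consistent reading is possible: a solicited seven-day question on five symptoms, with open adverse-event enquiry alongside it over the whole interval. At a day-28 visit the window does cover the first week at the full planned dose, which is itself an escalation step.

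A reader might also infer that the loss falls mainly on the metformin arm and makes the arms look alike. That direction is plausible for early symptoms caused by the drug. But the window is the same in both arms, and the protocol gives no onset, duration or frequency from which to show the effect or its size.

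The consequence is limited as well. Adverse events by group appear in the trial summary but not in the secondary endpoint list of section 2.2.2. No formal comparison is planned, and adherence is measured directly by diary and tablet count.

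These points remove the claims of exclusivity and of proven bias. They do not remove the conflict. The consistent reading is nowhere stated, and the wider routes are loosely specified: section 8.5 describes the diary as a record of drug intake, and section 9.2 has it reviewed at monthly visits only where there is one to review. The absence of formal testing does not protect a descriptive incidence from under-counting.

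**Conclusion.** The point holds as a conflict between collection rules with a definite gap in one of them. Taken alone, the section 9.1 window leaves 75% to 100% of the planned four-week escalation uncovered, always including weeks 1 and 2, and covers about 25% of treatment time thereafter. These figures rest on one month being 28 days and on the dose rising as scheduled. A woman who steps back a dose escalates over a longer period.

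If sites apply the seven-day rule, early transient symptoms will tend to be under-counted in the adverse-event incidence by arm. By how much is unknown, because it depends on symptom timing, symptom duration and how far the wider routes are used. It is not shown that the escalation goes unobserved or that tolerability will be overstated. The primary recruitment endpoint is unaffected. The correction should be made before data collection, since it cannot be made at analysis.

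**What to change.** Reconcile sections 9.1, 9.2, 10.2, 12 and 12.2 to one recall period for the five common symptoms: since the previous visit, or since first dose at the first visit. For each symptom record the onset date and the number of tablets per day being taken at onset. Section 12.3 already asks for onset date and dose for each adverse event, so this mainly aligns the symptom questionnaire with it. Use the diary as support where there is one, and state whether it is meant to record symptoms as well as tablets. If a measure of current symptoms is wanted, keep the seven-day item as a separate question and say that it does not limit adverse-event recording.

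The change is about one sentence in section 9.1 and one eCRF item. The costs are recall over about four weeks where the diary is missing or holds no symptoms, which matters in a population that includes women with low literacy, and more non-serious adverse events to enter. No dose or treatment rule changes.

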#### CONSENT

Women who are eligible and wish to participate (as described in paragraph 5.4 above) will be asked to sign a consent form. Eligibility will be formally confirmed by a suitably trained and delegated clinician. The original consent form(s) will be stored in the Investigator Site File (ISF) file, a copy is given to the woman, a copy added to the medical notes.

The consent log will be updated via the eCRF and following completion of the consenting procedures the following baseline assessments will be performed on participating women:

- Demographics
- Medical History including current pregnancy details, previous pregnancies, Height, Weight and Vital signs
- Preferred contact information

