# TABLE OF STUDY VISITS

Pregnancy gestation	1	2 +0 to 28	*  weeks	16, 20, 32, 36,40 weeks	24-30Weeks	Labour Delivery/	Neonatal/ 28 day postnatal
	Screenin	gConsen	Randomisation	Monthly	Study visit	Study visit	
Inc/Exc Criteria	х						
Patient Information Leaflet	х						
Consent Form		Х					
Demographics		x					
Medical History		Х					
Height and Weight		Х					
Vital Signs		x		x	х	х	
Confirm eligibility		x					
Randomisation			x				
Study Drug dispensed			х	x	х		
Review Patient Diary (collect at Delivery)				x	х	х	
Complete side effects questionnaire on eCRF				x	х	х	
Review and record pregnancy complications				x	х	х	
Review SAE's				x	х	х	x
Fasted glucose tolerance test (sampling at baseline and 2 hrs)					х		
Stored sample for inflammatory markers etc					х		
Unused Study Drug /packaging returned				x	х	х	
Labour/Delivery Information						х	
Neonatal/28 day postnatal complications and questionnaire							X

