#### 11.2 PROPOSED ANALYSES

The primary outcome is the ratio of women recruited, expressed as a fraction of the total number of women attending for antenatal care over the recruitment period. We will report this separately for the first 50 women, and the final 50 women in the primary recruiting site. The ratio of women recruited, expressed as a fraction of the total number of women attending for antenatal care over the recruitment period for the final 50 women in the primary recruiting site will be used to inform the timelines for a substantive trial.

Within the placebo group, we will determine the prevalence (with 95% confidence limits) of each of gestational diabetes and pregnancy induced hypertension.

We will generate mean (SD) or incidence of secondary outcomes overall, and in each of the two treatment groups. No formal statistical comparisons will be made between the two treatment groups, given the limitations of study power. A formal statistical analysis plan will be generated prior to study unblinding.

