#### **12.3.1 Pre-existing Medical Conditions**

Relevant pre-existing medical conditions (i.e. existed prior to informed consent) should be recorded as medical history and only recorded as adverse events if medically judged to have worsened during the study.

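### Section 9.1 reports five gastrointestinal symptoms as adverse events with no structured pre-dose record of them, and conflicts with the worsening rule in section 12.3.1

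*Protocol*

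**What the plan says.** Protocol section 9.1 names the commonest reactions to metformin as "nausea, vomiting, diarrhoea, abdominal pain and loss of appetite: most resolve spontaneously". It then says that the study will record, and report as AEs, "any of these symptoms that have been experienced during the seven day period, preceding the study visit".

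Section 12.3.1 treats relevant conditions that existed before consent as medical history, "only recorded as adverse events if medically judged to have worsened during the study".

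On what is collected before dosing:

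- Section 9.2, under Consent, states that "the following baseline assessments will be performed on participating women". The list is demographics, "Medical History including current pregnancy details, previous pregnancies, Height, Weight and Vital signs", and contact details. It has no symptom item.
- In the Table of Study Visits, the row "Complete side effects questionnaire on eCRF" is marked for the monthly, 24-30 week and labour/delivery columns. It is blank for screening, consent and randomisation.
- Section 10.2 says: "Participants will be asked about their well-being at each post-randomisation visit to identify side effects and any adverse events for reporting".
- Section 9.2 places the first monthly visit about one month after treatment starts, plus or minus seven days.

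On reporting, the Trial Summary lists adverse events by group as the last secondary endpoint. Section 11.2 gives secondary outcomes overall and by arm, and adds: "No formal statistical comparisons will be made between the two treatment groups".

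**The concern.** The participants are pregnant women enrolled from 12 weeks of gestation, and some may already have nausea, vomiting or poor appetite when they join. If such a symptom simply continues, section 9.1 makes it a reportable AE and section 12.3.1 does not. Staff at the two sites could each follow the protocol and record the same woman differently.

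Applying the worsening rule requires knowing how the woman was before the first dose. No structured enquiry supplies that. This is a gap in data collection, so a later analysis plan cannot fill it. At stake is the per-arm incidence of these symptoms, one of the figures the feasibility study hands to the designers of the main trial.

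**Working it through.** The protocol states no figure for symptom prevalence or AE incidence, so there is nothing to reproduce. The check is a comparison of the text, followed by an illustration on assumed rates.

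**1. The two rules on one case.** A woman has nausea before consent and the same nausea in the week before her first monthly visit. Section 9.1 says AE. Section 12.3.1 says medical history, and not an AE because it has not worsened.

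**2. Can the look-back reach the pre-dose period?** With a 28-day interval and a 7-day tolerance, the earliest first monthly visit is about day 28 − 7 = 21. Seven days of recall then start at about day 21 − 7 = 14, after the first dose. On the section 8.3 schedule, the daily dose has been raised three times by week 4. The questionnaire therefore never observes the untreated state.

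**3. Scope of the rule.** It covers five named symptoms in a window of 7/28 = 25% of treatment time (7/35 = 20% to 7/21 = 33% as visit spacing varies). It is not a record of every symptom on treatment. Section 12.2 adds open-ended AE enquiry.

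**4. Illustration.** Inputs:

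- From section 11.1: 50 women per arm.
- Assumed: a share b with at least one of the five symptoms at entry that persists unchanged to a visit, taken as 10%, 30% or 50%.
- Assumed: new-onset rates a of 30% on metformin and 10% on placebo, a true difference of 20 points.

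Formulas: women carried over per arm = 50b; recorded incidence = b + (1 − b)a; recorded difference = (1 − b)(0.30 − 0.10).

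| b | carried over per arm | metformin recorded | placebo recorded | difference |
|---|---|---|---|---|
| 10% | 5 | 0.10 + 0.90 × 0.30 = 37% | 0.10 + 0.90 × 0.10 = 19% | 18 points |
| 30% | 15 | 0.30 + 0.70 × 0.30 = 51% | 0.30 + 0.70 × 0.10 = 37% | 14 points |
| 50% | 25 | 0.50 + 0.50 × 0.30 = 65% | 0.50 + 0.50 × 0.10 = 55% | 10 points |

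Both arms' figures rise and the contrast shrinks. Neither arm is favoured by design.

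**5. Chance imbalance at entry.** The 95% half-width for the between-arm difference in b is 1.96 × √(2b(1 − b)/50):

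- b = 10%: 1.96 × √0.0036 = 11.8 points
- b = 30%: 1.96 × √0.0084 = 18.0 points
- b = 50%: 1.96 × √0.0100 = 19.6 points

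Recorded incidence can be rewritten as a + b(1 − a). An imbalance d, split evenly between the arms, therefore moves the recorded difference by d × (0.70 + 0.90)/2 = 0.8d, that is 9.4, 14.4 or 15.7 points. Against recorded differences of 18, 14 and 10 points, this is about half the difference at b = 10%, about equal to it at 30%, and larger than it at 50%. This is ordinary sampling variation and not bias, but without a baseline it cannot be seen or separated.

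**The case against.** The protocol is better protected than a quick reading suggests, and several stronger statements that a reader might infer are not supported.

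- *Symptoms are never recorded before the first dose.* Not so. The baseline history includes details of the current pregnancy, and nausea could be noted there. Section 12.3 requires an onset date and severity for each AE, and section 8.2 provides for dose administration to be recorded in the diary. What is absent is a structured record.
- *The worsening rule cannot be applied.* Too strong. Section 12.3.1 rests on medical judgement, which can use history, onset and severity. But an onset date recalled weeks later gives no contemporaneous pre-dose severity, so the rule can be applied only unreliably.
- *Existing symptoms are counted as side effects.* Section 12.1 defines an AE without implying cause, and causality is judged separately in section 12.5.2. The protection is partial. Section 12.4 assesses all events as though the woman were on metformin, and a possible relation is enough for an adverse reaction.
- *Each arm's incidence stands alone.* A blinded, concurrent placebo figure is reported beside the metformin figure and shows the average background. The absence of a formal test does not change that.
- *Tolerability is a main result.* The primary endpoint is the recruitment ratio. Section 2.2.2 does not list AEs; only the Trial Summary does, last.

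It can also be argued that section 9.1 says only what to ask and section 12.3.1 supplies the exception. That is a reasonable reading, but section 9.1 also says what is reported as an AE and makes no cross-reference, so sites are left to infer it. Finally, section 12.2 favours recording in cases of doubt. That argues against any fix that would drop symptoms from the record.

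**Conclusion.** The point holds in a limited form. Sections 9.1 and 12.3.1 give different answers for a pre-existing symptom that continues unchanged, and the schedule contains no structured symptom enquiry before the first dose. The worsening rule can therefore be applied only unreliably, and the per-arm incidence of these symptoms mixes what women brought with them and what began on treatment.

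The size is unknown. The protocol gives no entry rate, and the figures of 5 to 25 women per arm, or a 20-point difference shrinking to between 18 and 10, depend wholly on assumed entry, persistence and new-onset rates. The conflict and the missing baseline do not depend on them. The primary endpoint is unaffected. This is a low-cost improvement to a secondary safety summary, and it has to be made at the data-collection stage.

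**What to change.** 1. Give the existing side-effects questionnaire, with the same 7-day recall, once at the consent visit before the first dose. Add it to the baseline list under Consent in section 9.2 and to the consent column of the Table of Study Visits. Section 10.2 should mention this pre-dose enquiry.
2. Reconcile section 9.1 with section 12.3.1, by cross-reference or rewording, so that one stated rule governs symptoms present before treatment.
3. Keep recording every reported symptom, in line with the inclusive approach of section 12.2. For each arm, report both the crude incidence and the incidence of symptoms new or worse than at baseline.

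The cost is a few more minutes per woman at a visit that already takes place, one additional eCRF page, and short edits to the sections named. No treatment rule changes.
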